2. SYNOPSIS

Trial Title	Oxford Acute Myocardial Infarction - Pressure-controlled Intermittent Coronary Sinus Occlusion in STEMI
Internal ref. no. (or short title)	OxAMI-PICSO
Clinical Phase	II
Trial Design	Prospective single centre observational cohort study

Trial Participants	Patients admitted for primary percutaneous coronary intervention for ST elevation myocardial infarction	
Planned Sample Size	75 patients	
Treatment duration	Maximum of 90 minutes	
Follow up duration	6 months	
Planned Trial Period	18 months	
	Objectives	Outcome Measures/Endpoints
Primary	To evaluate the effect of pressure intermittent controlled coronary sinus occlusion on the indexes of coronary physiology and on infarct size in STEMI patients at short and mid term follow up.	To evaluate the effect of pressure intermittent controlled coronary sinus occlusion on infarct size measured at cardiac magnetic resonance after 24-48 hours from revascularization.
Secondary	To evaluate the utility of individual biomarkers (blood components derived substances from cells, DNA, plasma etc) in the assessment of coronary artery disease and myocardial infarction investigating also how these individual biomarkers may be modified by PICS0 treatment.	To evaluate the effect of pressure intermittent controlled coronary sinus occlusion on humoral biomarkers and on the evolution of parameters of coronary physiology at 24 hours and infarct size, microvascular obstruction at cardiac magnetic resonance after 6 months from revascularization.
Safety Endpoint	To evaluate the rate of PICS0 failure deployment, coronary sinus complications, and additional time and radiation exposure associated to for PICS0 deployment	
Device name	Pressure intermittent controlled coronary sinus occlusion (PICS0)	
Device Manufacturer	Miracor Medical System	
Device Classification	Interventional Cardiology	

Protocol version no.	Effective Date	Significant Changes	Previous protocol version no.
2.0	01.04.2015	- Clarification of follow up duration - Clarification for what group of patient CMR follow up is meant	v1.0 13.02.2015
3.0	20.06.2016	- Extension of sample size to 75 patients to achieve a minimum of 25 patients with complete dataset	v2.0 01.04.2015

Protocol version no.	Effective Date	Significant Changes	Previous protocol version no.
4.0	06.05.2016	
 - Change in information about regulatory status of PICSO technology from CE-marked to non non-CE mark - Extension of recruitment beyond the period specified in the IRAS application form 	V3.0 20.06.2016
5.0	26.02.2018	
 - Extension of recruitment beyond the period specified in the IRAS application form - Extension of inclusion criteria to allow enrolment of all patients with ST elevation myocardial infarction, irrespectively of the coronary location of the culprit lesion 	V4.0 06.05.2016

3. ABBREVIATIONS

AE	Adverse event
AR	Adverse reaction
CFR	Coronary flow reserve
CI	Chief Investigator
CMR	Cardiac magnetic resonance
CRA	Clinical Research Associate (Monitor)
CRF	Case Report Form
CRO	Contract Research Organisation
CT	Clinical Trials
DMC/DMSC	Data Monitoring Committee / Data Monitoring and Safety Committee
FFR	Fractional flow reserve
GCP	Good Clinical Practice
GP	General Practitioner
ICF	Informed Consent Form
ICH	International Conference of Harmonisation
IMR	Index microcirculatory resistance
IRB	Independent Review Board

MI	Myocardial infarction
NHS	National Health Service
NRES	National Research Ethics Service
PCI	Percutaneous coronary intervention
PI	Principal Investigator
PICSO	Pressure controlled intermittent coronary sinus occlusion
PIL	Participant/ Patient Information Leaflet
R&D	NHS Trust R&D Department
REC	Research Ethics Committee
SAE	Serious Adverse Event
SAR	Serious Adverse Reaction
SDV	Source Data Verification
SOP	Standard Operating Procedure
SUSAR	Suspected Unexpected Serious Adverse Reactions
TMF	Trial Master File
TSG	Oxford University Hospitals Trust / University of Oxford Trials Safety Group

4. BACKGROUND AND RATIONALE

Restoration of blood flow in the infarct related artery (IRA) is the cornerstone for the current treatment of ST elevation myocardial infarction (STEMI) [1]. However in a variable proportion of patients, ranging from 30 to 40%, myocardial reperfusion is impaired, despite the apparent successful achievement of epicardial coronary artery patency [2]. This condition, known as no reflow, is due to microvasculature dysfunction and/or obstruction and it is the result of the interaction of several pathophysiological mechanisms including ischemia injury, reperfusion injury, distal embolization and tissue oedema [3].

4.1 Diagnosis of no reflow

Identification of no reflow and microvascular obstruction can be obtained by application of different diagnostic tools. So far cardiac magnetic resonance (CMR) represents the gold standard for detection and quantification of myocardial damage and microvascular impairment [4]. Parameters easily derived from

CMR such as infarct size, area at risk, myocardial salvage and microvascular obstruction have been shown to be related to long term outcome.

A major limitation of CMR is the time-delay from percutaneous coronary intervention (PCI), being applied at the earliest at the end of the revascularization procedure [4]. Early identification of patients at higher risk of no reflow, during the PCI procedure, would be extremely useful and in such regard parameters of coronary physiology may have a role. Indeed, measurements of blood flow and coronary microcirculation function are now used in the catheter lab during routine PCI, using standard techniques (a pressure wire) that are incorporated into the PCI procedure itself (by replacing the PCI procedure wire with a pressure wire). An example of this is the measurement of the index of microcirculatory resistance (IMR), defined as distal coronary pressure divided by the inverse of the hyperaemic mean transit time (a correlate to absolute flow). It is measured simultaneously with the coronary pressure wire and it evaluates microvascular resistance, independently of epicardial stenosis [5]. IMR has become the catheter-based method of choice to independently assess coronary microcirculation [5-6]. Recent data suggest that IMR, measured acutely in patients with MI undergoing emergency PCI, provides useful prognostic information [7]. Specifically, a postprocedure IMR > 40 has been shown to be significantly associated with a worst long term prognosis in terms of cardiac death and re-hospitalization for heart failure [8].

We have conducted a preliminary study, in the setting of the Oxford Acute Myocardial Infarction (OxAMI) project, to understand the procedural aspects at PCI that may directly influence the microcirculation. The key findings are that:

1. Coronary stenting itself reduces IMR and is thus beneficial in terms of the microcirculation.
2. Patients with a low pre-stenting IMR tend to do have little change in IMR.
3. Conversely the reduction in IMR is largest in those with a higher IMR (> 40) before stenting
4. However, a proportion of patients with high IMR can continue to have a still high (> 40) or even further increased poststenting IMR.

This suggests that patients with a high pre-stenting IMR are at especially higher risk and may benefit from additional interventions.

4.2 Retroperfusion strategy and PICSO

So far many strategies have been proposed in order to prevent and/or to treat no reflow, but none have demonstrated a consistent beneficial effect. A new proposed approach being investigated is the retroreperfusion strategy [9] based on the principle that it is possible to reduce the ongoing ischemia by perfusing the myocardium through the coronary sinus.

The concept of retroperfusion is 100 years old it has been initially discarded after the advent of coronary artery bypass grafting and PCI. Different techniques of retroperfusion are available: intermittent coronary sinus occlusion (ICSO), synchronized retrograde perfusion (SRP) and simplified retroperfusion (SR) [10-13]. The common denominator is the temporal increase in coronary sinus pressure through the coronary sinus occlusion (ICSO) or retroperfusion with arterial blood (SRP and SR).

PICSO is a modification of the original time-dependent ICSO and it is applied through a dedicated catheter (PICSO Impulse catheter, Mirarcor Medical System GmbH, Vienna, Austria).

The catheter presents a balloon at the distal end. The balloon inflates and deflates cyclically once deployed in the coronary sinus, leading to intermittent coronary sinus pressure increase. This intermittent increase in coronary sinus pressure leads to an improved perfusion of the ischemic area with potential benefit in terms of myocardial salvage through 3 mechanisms: 1) redistribution of blood flow from the remote myocardium to the border zone of the ischemic myocardium [14]; 2) enhanced wash out of noxious, inflammatory factors and embolic material across the microvascular bed (suction effect upon balloon release) [15]; 3) improvement in collaterals through release of vascular growth factors as consequence of venous pressure increase [16-17].

The PICSO technology has revealed to be effective in several models by reducing infarct size (IS) [18] and a metanalysis on seven studies on animal models has confirmed a statistically significant -29% (CI95% - 40.9 – -17.7, p<0.001) reduction in IS compared to control group [19]. Moreover, it has also been shown that the benefit from PICSO treatment is directly proportional to the pressure reached in the coronary sinus during the balloon inflation and thus to the increase in coronary wedge (CW) pressure, which is the pressure associated to the blood flow provided to the ischemic region by collateral branches [20].

The Prepare-PICSO study represents the first-in-man experience with the PICSO device [21]. On a small sample of 15 patients with stable angina the PICSO treatment showed to be firstly safe and, as observed in the animal models, was associated to a significantly increase in coronary sinus pressure as well in mean CW pressure in the distal left anterior descending (LAD) coronary artery [21].

These findings have triggered the Prepare-RAMSES study in which PICSO treatment was investigated for the first time in man in patients with STEMI [22]. The results of the study have been recently published. The study was initially designed to include 30 patients with anterior STEMI with PICSO treatment for 90 minutes after the completion of primary percutaneous coronary intervention (PPCI). The study enrolled only anterior STEMI since expected to be responsive to the PICSO device, being mainly the anterior wall of the myocardium drained by the coronary sinus. The device resulted to be safe, with a median implantation time of 12 minutes. The primary endpoint was the reduction in IS at cardiac magnetic resonance (CMR) at 2-4 days and 4 months. The PICSO group was compared with a matched control group of patients.

Although the study did not show an overall difference in the reduction in IS in the PICSO group [22], IS reduction appeared to be significantly related to the quantity of PICSO treatment (pressure achieved in the coronary sinus x time of treatment) and significantly higher in the small subgroup of patients receiving high PICSO quantity.

It is possible that the study did not reach the primary endpoint due to some limitations in its design. First of all the small sample size has to be acknowledged, since the investigators managed to fully deliver the PICSO treatment only to 12 patients (63% of the initially intended sample size). Moreover, the study

presented a potential “selection bias” that drove the investigators to include in the study “relatively healthier” patients in which anticipated benefit was limited: 40% of patients enrolled presented with a Thrombolysis In Myocardial Infarction (TIMI) flow > 1, e.g. presented with an open coronary artery at the time of primary PCI. Moreover the application of PICSO treatment at the end of the PPCI may have blunted the expected benefit: the device was deployed after stenting, the stage the procedure known to be at higher risk of distal embolization of atherothrombotic debris downstream the coronary microvasculature [22].

Identification of “higher risk” STEMI patients is thus crucial in order to confirm a clear benefit associated to the PICSO device.

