6. TRIAL DESIGN

The OxAMI-PICSO study is a prospective single centre observational cohort study of the use of PICSO in patients presenting for primary PCI for acute myocardial infarction. The OxAMI- PICSO study is based upon the established framework of the OxAMI study (Ethics Ref 11/SC/0397).

Patients, age 30-90, presenting with ST elevation myocardial infarction will be considered for inclusion in the study. Measurement of IMR before stenting is an essential prerequisite for the study: only patients with pre-stenting IMR > 40 will be considered eligible for the PICSO treatment. Patients with IMR≤ 40 will remain in the study but will not undergo PICSO treatment. The procedure for consent in patients undergoing emergency PCI will be as already established in the ongoing OxAMI study, and is discussed below in Section 8.1.2.

The PCI procedure will be undertaken in a standard fashion, and include the use of pressure wire measurements before and after stent deployment. Aspiration or distal protection devices may be used if clinically indicated and where vessel anatomy is suitable. The devices used and the procedural techniques will be driven by clinical decision making at the patient and institutional level, and carried out in accordance with the Oxford University Hospitals NHS Trust (OUHT) departmental guidelines for PCI.

PICSO treatment will be added on top of the conventional treatment.

The protocol will constitute of 5 main stages described in details in the next sections (Section 8.3).

Only patients with pre-stenting IMR > 40 and who assent to receive PICSO treatment will undergo 24 hours coronary angiogram with coronary physiology measurement, 24-48 hours CMR scan and 6 months CMR scan. Patients who assent to participate in the study but in whom the pre-stenting IMR ≤ 40, or those in whom the pre-stenting IMR > 40 but the participant declines PICSO treatment will remain in the study for blood sampling and clinical data collection at the same follow up time points (24 hours, 48 hours and 6 months). A summary of the study design, indicating the time points and procedures, is shown in Section 8.3.

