7.2. Inclusion Criteria

Participants must satisfy the following conditions:

- Male or Female, aged 30 to 90 years,
- Clinical presentation with STEMI
- Referred for coronary angiography with view to proceed to PCI with stenting.

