7.3. Exclusion Criteria

The participant may not enter the study if ANY of the following are known to apply:

- Patients in whom safety or clinical concerns preclude participation.
- Known anaemia (Hb <9).
- Pregnant or breast feeding females.
- Revascularization by mean of balloon angioplasty without stenting
- History of stroke, TIA or reversible ischemic neurological disease within last 6 months
- Known severe renal failure (eGFR < 30 ml/min/1.73m²) or history of dialysis or renal transplant
- Previous coronary bypass artery grafting
- Known severe valvular abnormalities
- Previous STEMI presentation
- Presentation with cardiogenic shock
- Severe bradycardia (Heart rate < 50 beats per minutes)
- STEMI due to stent thrombosis
- Unconscious on presentation

- Non-cardiac comorbidities and life expectancy < 1 year
- Use of warfarin
- Presence of pacemaker or other electrodes in the coronary sinus
- Contraindications to adenosine
- Additional exclusion criteria for participants undergoing CMR
 - claustrophobia which limits / prevents participants from remaining in CMR scanner.
 - patients who cannot lie flat on the scan table.
 - patients with metallic implants, pacemakers, implantable defibrillators etc, unless known to be CMR compatible.
 - patients with known allergy to medium of contrast (gadolinium)

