8.3.1 Stage 1: Pre-Stenting

- Diagnostic angiography will be performed in the standard manner using appropriate catheters.
- Bivalirudin will be administered (0.75mg/kg bolus followed by an infusion of 1.75 mg/kg/min for up 4 hours after the procedure as clinically warranted), as routinely used for PCI. The lesion will be

crossed with a coronary guide wire in the usual manner for PCI. Normal blood flow will be rapidly achieved by thrombus aspiration and/or predilation

3. Pre-stenting coronary physiology parameters, namely FFR, CFR and IMR, will be measured, using a pressure wire, as used for routine clinical measurements in patients undergoing PCI.
4. If pre-stenting IMR is > 40 , patients will be invited to receive the PICSO device. If pre-stenting IMR is ≤ 40 PICSO device will not be proposed, but the patient will be invited to remain in the study for serial blood sampling (procedural-6 hours-24 hours and 48 hours) and routine clinical data collection.

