12.2 Analysis of Endpoints

In keeping with our usual practice we will obtain expert statistical advice from the Centre for Statistics in Medicine (or equivalent) for each specific task. Summary statistics, including means, medians, and

variances, will be calculated at each time point and for each type of data (e.g. parameters derived from coronary physiology and CMR). The distribution of the levels will be described. It may be necessary to log transform the data before further statistical analysis. For each parameter an analysis of variance will be carried out at each time point.

Control group in OxAMI-PICSO study is represented by a highly matched group of patients underwent to primary PCI, with a prestenosing IMR > 40 and with available 24 hours recath and 24-48 hours/6 months CMR data. Matching will be performed by application of a propensity score matching analysis including the following predictors in the model: age, sex, pain to wire time, thrombotic burden (assessed as angiographic thrombus score), thrombus aspiration performance, stent volume, glycoprotein IIbIIIa inhibitors adoption.

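### Initial TIMI flow, which the protocol's background treats as marking lower-risk patients, is left out of the propensity score, so residual confounding of the infarct-size comparison is possible

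*Combined protocol and SAP*

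**What the plan says.** Section 4.2 reviews the predecessor study of PICSO in anterior STEMI, which found no overall difference in infarct-size reduction. It offers a hedged explanation: "It is possible that the study did not reach the primary endpoint due to some limitations in its design". Three limitations follow: the small sample, a potential selection bias, and deployment of the device after stenting. The evidence given for the second is that "40% of patients enrolled presented with a Thrombolysis In Myocardial Infarction (TIMI) flow > 1"; the protocol describes the result as inclusion of comparatively healthy "patients in which anticipated benefit was limited".

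The present study answers the low-risk problem by selecting on microvascular resistance. Section 6 states that "only patients with pre-stenting IMR > 40 will be considered eligible for the PICSO treatment", and sections 4.3 and 12.2 apply the same threshold to the controls. Section 8.3.1 places the IMR measurement after this step: "Normal blood flow will be rapidly achieved by thrombus aspiration and/or predilation".

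Initial flow is not an entry rule. Section 7.2 asks for age 30 to 90, "Clinical presentation with STEMI" and referral for angiography with a view to stenting. Section 7.3 begins "The participant may not enter the study if ANY of the following are known to apply", and its list contains nothing on vessel patency or TIMI flow.

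Controls are historical patients from the OxAMI study, matched by propensity score (sections 10.1 and 12.2). The predictors are "age, sex, pain to wire time, thrombotic burden (assessed as angiographic thrombus score), thrombus aspiration performance, stent volume, glycoprotein IIbIIIa inhibitors adoption". The only inferential method that section 12.2 names is an analysis of variance for each parameter at each time point. No covariate adjustment is described.

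**The concern.** The background uses flow at presentation to separate lower-risk from higher-risk patients. It is fixed before any study treatment and is seen on the first angiogram. The matching in section 12.2 is the only confounding control stated beyond the shared IMR threshold, and it omits this variable. If the PICSO group and the matched controls differ in the share of arteries open on arrival, part of any difference in infarct size at 24–48 hours could reflect that mix. More open arteries in the PICSO group would exaggerate benefit; more among controls would hide it.

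This is a different problem from the one section 4.2 describes. There, open arteries diluted the expected benefit. Here they would act as a confounder, and only if the two groups are unbalanced on them.

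**Working it through.** **1. What each existing safeguard records.**
- IMR above 40 is required in both groups, but it is measured after aspiration and/or predilation has restored flow. It describes the microcirculation at that moment, not patency on arrival. It enters as a threshold only; its value is not in the score.
- Pain-to-wire time equals occlusion time only if the artery stayed closed. In a patient with an open artery it does not.
- Thrombus score and use of aspiration plausibly carry some information on initial flow. The scoring scale is not described, and neither is said to record flow.

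**2. The plan's own figure.** Section 12.1 gives 12 per group for a 29% reduction at 95% confidence and 80% power, raised to 25 per arm. No SD or control mean is stated, so the 12 cannot be reproduced. The coefficient of variation (CV) it implies, two-sided with a normal approximation, follows from n = 2(1.960 + 0.842)² × CV² / 0.29²:

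CV = (0.29 / 2.802) × √(12/2) = 0.254.

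Step 5 uses CV 0.25, and 0.50 as an assumed wider value.

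**3. Size of a spurious difference.** Set mean infarct size with an occluded artery to 1 and with an open artery to 1 − r. With open-artery shares p_T (PICSO) and p_C (control) and no true effect:

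spurious relative difference = (1 − r·p_T) / (1 − r·p_C) − 1.

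Assumptions, none from the documents: r = 0.20 to 0.40; shares of 40% and 20%; flow unrelated to the matched variables, so the proxies give no help.

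| r | PICSO open | Control open | Calculation | Spurious difference | Share of 29% |
|---|---|---|---|---|---|
| 0.20 | 40% | 20% | 0.92/0.96 − 1 | −4.2% | 14% |
| 0.40 | 40% | 20% | 0.84/0.92 − 1 | −8.7% | 30% |
| 0.20 | 20% | 40% | 0.96/0.92 − 1 | +4.3% | 15% |
| 0.40 | 20% | 40% | 0.92/0.84 − 1 | +9.5% | 33% |

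With a true 29% reduction, the first two rows would show 32.0% and 35.2% (for example 1 − 0.71 × 0.92/0.96). The last two would show 25.9% and 22.2%.

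**4. Could a 20-point gap arise?** With 25 per arm and the same underlying share in both groups, the 95% range of the difference by chance is 1.96 × √(2p(1 − p)/25). This is ±22 points at p = 0.20 and ±27 points at p = 0.40. A gap of this size would be unremarkable even without systematic selection. On average the standard error already allows for chance gaps; it does not allow for a systematic one.

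**5. Effect on the test if the gap were systematic.** Two-sided z-test, 25 per arm, no true effect, standard error = CV × √(2/25). For the first two rows of the table, the probability of a significant result rises from 5% to 9% and 23% at CV 0.25, and to 6% and 9% at CV 0.50.

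**The case against.** The strongest reply is that the protocol has already dealt with low-risk patients, by a different route. Section 12.1 presents IMR selection as the answer to that limitation, section 4.3 links high pre-stenting IMR to larger infarcts, and the threshold binds both groups. Patients with an open artery may be uncommon above IMR 40. Thrombus score, aspiration and pain-to-wire time are matched as well. A reader might infer that nothing corrects for initial flow; the documents do not support that. What stands after this reply is narrower: the proxies are indirect, nothing shows that they are sufficient, and an imbalance could remain.

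A reader might also infer that the protocol names initial flow as a determinant of infarct size, or firmly blames it for the predecessor's result. It does neither. It speaks of healthier patients with limited expected benefit, as one possible explanation among three.

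The illustration is open to challenge too. Its inputs are assumed, and it gives the bias before any help from the proxies. A larger gap is easy to compute: 60% open against 20% would give 1 − 0.88/0.96 = 8.3% to 1 − 0.76/0.92 = 17.4%. But 60% exceeds the 40% seen in the predecessor, and here it would have to arise after selection on IMR. That case should not be relied on.

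Finally, any short propensity list leaves out something prognostic. That is true, but this variable is one that the protocol itself uses to distinguish patients.

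**Conclusion.** The point holds as one of possible residual confounding. Initial TIMI flow is absent from entry, matching and the stated analysis, although the background uses it to characterise risk; the available proxies are partial. The documents do not show that the two cohorts differ in initial flow, so they do not support a claim that the comparison is biased, or in which direction.

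Under the stated assumptions and a 20-point gap, the spurious difference is 4.2–8.7% if open arteries are commoner in the PICSO group and 4.3–9.5% if they are commoner among controls. That is roughly one seventh to one third of the planned 29%: not enough to create the whole effect, but enough to matter with 25 per arm. Any information in the proxies would shrink it. This is a worthwhile, inexpensive improvement rather than a fatal flaw.

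**What to change.** In section 12.2:

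- Add TIMI flow on the first diagnostic angiogram, before aspiration or predilation, grouped 0–1 v 2–3, to the propensity model.
- Report its distribution in the PICSO group and the matched controls, with the balance after matching.
- Prespecify a sensitivity analysis of infarct size at 24–48 hours that extends the planned analysis of variance with initial flow as a covariate.

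The baseline split is useful even if the groups prove balanced: by the protocol's own reasoning, initial flow bears on how much benefit could be expected.

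This assumes that initial flow can be read from the diagnostic angiograms or catheter reports of the OxAMI controls. The documents do not say so, and it should be confirmed first. The cost is that reading and an eighth term in a propensity model with about 25 treated patients, which may slightly reduce the number of acceptable matches. Entry criteria and sample size do not change.
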